### **9.2 SETTING**

#### **9.2.1 Definitions**

Study Period: the period of time that includes the exclusion criteria assessment period, baseline, cohort entry date, and follow-up period for the study population. This period is the same for all patients.

The study period will be from 1 January 2008 to 31 March 2018, encompassing date of the earliest data availability to the date of the latest data availability.

Patient Selection Period: the period of time for which patients are eligible to enter the cohort. The earliest date of the patient selection period is 17 November 2015, corresponding to 180-days after US approval date of Stiolto Respimat.

Cohort Entry Date: Date of entry to the initial cohort of Stiolto or Anoro users.

[figure not shown]
Baseline Period: the 180-day period that ends 1 day prior to the cohort entry date used to assess covariate information. The baseline period will vary between patients depending on these dates. The earliest start of the baseline period would be 21 May 2015, the date of Stiolto approval (i.e. 180 days before November 17, 2015).

Follow-Up Period: the period of time between 1 day after the cohort entry date to the earliest occurrence of the outcome (discontinuation of refills), or any censoring criteria (365 days, death, disenrollment, or end of data). Addition of another treatment in addition to index treatment will not count as discontinuation.

For entry into the study population, patients will be required to have 180 days of continuous enrolment with both medical and pharmacy coverage. Data during the baseline period will be used to confirm study eligibility and classification of incident COPD. The follow-up period will be used for capturing first and second maintenance therapies. This is illustrated in **Figure 1**.

Figure 1

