## Study timeline for the Primary Study Population

## 9.2.2 Study population

The pre-matched study cohort will consist of patients initiating Olodaterol/Tiotropium Bromide or Umeclidinium/Vilanterol between 17 November 2015 and 31 March 2018.

The following exclusion criteria will then be applied:

Aged <40 years.

Enrolment with medical and pharmacy coverage prior to the cohort entry < 180 days.

Never had COPD diagnosis on the cohort entry date or prior to cohort entry.

A record for dispensed Olodaterol/Tiotropium Bromide delivered with Respimat inhalator or Umeclidinium/Vilanterol delivered with the Ellipta Inhaler during the 180-day baseline prior to cohort entry.

[figure not shown]
Diagnosis of asthma any time prior to cohort entry.

Diagnosis of lung cancer any time prior to cohort entry.

Diagnosis of lung transplant any time prior to cohort entry.

Figure 2

Below depicts the flow diagram of patients.

Diagnosis of COPD (ICD-9: 491.\*, 492.\*, 496.\*; ICD-10: J41.0, J41.1, J41.8, J42.\*, J43.0, J43.1, J43.2, J43.8, J43.9, J44.0, J44.1, J44.9) will be defined as the presence of an inpatient or outpatient claim.

Diagnosis of asthma (ICD-9: 493.\*; ICD-10: J45, J45.20, J45.21, J45.22, J45.90\*, J45.99\*) will be defined as either 1 inpatient claim or 2 outpatient events 30-365 days apart.

Diagnosis of lung cancer (ICD-9: 162.2, 162.3, 162.4, 162.5, 162.8, 162.9, 231.2; ICD-10: C34.00, C34.01, C34.02, C34.10, C34.11, C34.12, C34.2, C34.30, C34.31, C34.32, C34.80, C34.81, C34.82, C34.90, C34.91, C34.92, C7A.090, D02.20, D02.21, D02.22, Z85.118) will be defined as either 1 inpatient claim or 2 outpatient events 30-365 days apart.

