#### **9.3.3 Covariates**

Covariates will be identified based on data recorded within 180 days prior to or on the index date (date of dispensing/initiation of the exposure), unless otherwise specified. If multiple measurements are made in the baseline period, then the most recent measurement will be used.

Covariates will be used to predict propensity scores in later analyses. Absolute and relative frequencies of each covariate will also be reported in Table Shells 1 and 2 (see [Annex 5](#)). Detailed descriptions of the listed covariates can be found in [Annex 3](#) and [4](#).

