Charlson-Deyo Comorbidity Index	
This measure computes a score by summing over the following components:
 
 
· If the event Acute Myocardial Infarction Occurs within 180 days, set the score to 1.0 Otherwise, set the score to 0.0
 
· If the event Heart Failure Occurs within 180 days, set the score to 1.0 Otherwise, set the score to 0.0
 
· If the event Peripheral Vascular Disease Occurs within 180 days, set the score to 1.0 Otherwise, set the score to 0.0
 
· If the event Cerebrovascular Disease Occurs within 180 days, set the score to 1.0 Otherwise, set the score to 0.0
 
· If the event Dementia Occurs within 180 days, set the score to 1.0 Otherwise, set the score to 0.0
 
· If the event Chronic Obstructive Pulmonary Disease Occurs within 180 days, set the score to 1.0 Otherwise, set the score to 0.0
 
· If the event Rheumatologic Disease Occurs within 180 days, set the score to 1.0 Otherwise, set the score to 0.0
 
· If the event Peptic Ulcer Disease Occurs within 180 days, set the score to 1.0 Otherwise, set the score to 0.0
 
· If the event Hemiplegia or Paraplegia Occurs within 180 days, set the score to 2.0 Otherwise, set the score to 0.0
 
· If the event Renal Disease Occurs within 180 days, set the score to 2.0 Otherwise, set the score to 0.0
 
· If the event HIV/AIDS Occurs within 180 days, set the score to 6.0 Otherwise, set the score to 0.0
 
· For the measure Cancer use the value of the measure as the score multiplied by weight 1.0 If the value is missing, set the score to 0.0
 
· For the measure Diabetes use the value of the measure as the score multiplied by weight 1.0 If the value is missing, set the score to 0.0
 
· For the measure Liver Disease use the value of the measure as the score multiplied by weight 1.0 If the value is missing, set the score to 0.0
 

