## **ANNEX 5. TABLE SHELLS AND PROPOSED FIGURES**

**Table 1.** Cohort Selection

	Excluded	Remaining
Eligible Population		
Did not meet cohort entry criteria (use of Tio/Olo or Ume/Vi)		
< 180 days of continuous enrollment		
Prior use of Ume/Vi during 180d washout		
Prior use of Tio/Olo during 180d washout		
Tio/Olo and Ume/Vi both occurring on cohort entry date		
Age <40 years		
No prior diagnosis of COPD any time prior using all available data		
Diagnosis of Asthma any time prior using all available data		
Diagnosis of Lung Cancer any time prior using all available data		
Lung Transplant any time prior using all available data		
Final cohort		

**Table 2.** Patient Characteristics of the Study Population (Unmatched/ Matched)

	Tio/Olo	Umech/Vi	Standardized Difference (95% CI)
N			
Median Follow-up Time [IQR]			
Demographics			
Age on index date			
Mean (SD)			
Median [IQR]			
Gender			
Male; n (%)			
Female; n (%)			
Region			
Northeast; n (%)			
North Central; n (%)			
South; n (%)			
West; n (%)			
Missing/Unknown; n (%)			
Insurance Type			
Commercial; n (%)			
Medicare; n (%)			
Missing; n (%)			
Year of Cohort Entry, n (%)			
First Year (November 17, 2015 – November 30, 2016); n (%)			
Second Year (December 1, 2016 – November 30, 2017); n (%)			
Third Year (December 1, 2017 to March 31, 2018)			
Concomitant Medications			

Proprietary confidential information © 2019 Boehringer Ingelheim International GmbH or one or more of its affiliated companies

	Tio/Olo	Umec/Vi	Standardized Difference (95% CI)
Oral Corticosteroids; n (%)			
Short acting muscarinic antagonist (SAMA), n (%)			
Short acting beta agonist (SABA), n (%)			
Long acting muscarinic antagonist (LAMA), n (%)			
Long acting beta agonist (LABA), n (%)			
Inhaled corticosteroid (ICS), n (%)			
LAMA / LABA combination (not Tio/Olo or Umec/Vi), n (%)			
LABA / ICS combination, n (%)			
LAMA / LABA / ICS combination, n (%)			
NSAIDs, n (%)			
Antihistamines, n (%)			
Opioids, n (%)			
Oral antibiotics, n (%)			
Antidiabetic Agents (not including insulin), n (%)			
Insulin (basal or mealtime), n (%)			
Methotrexate, n (%)			
Statins; n (%)			
Antihypertensives; n (%)			
Anticoagulants; n (%)			
Anti-psychotic/anti-depressives/anxiolytic, n (%)			
Oxygen therapy, n (%)			
Comorbidities/Symptoms			
History of All-Cause Hospitalization; n (%)			
History of Emergency Department Visit; n (%)			

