History of Hospitalization due to Respiratory Condition; n (%)			
Acute Myocardial Infarction; n (%)			
Angina Pectoris; n (%)			
Peripheral Vascular Disease; n (%)			

	Tio/Olo	Umech/Vi	Standardized Difference (95% CI)
Heart Failure; n (%)			
Hypertension; n (%)			
Upper Respiratory Tract Infection; n (%)			
Lower Respiratory Tract Infection; n (%)			
Cardiac Arrhythmias; n (%)			
Cerebrovascular Disease; n (%)			
All Cancers (except non-melanoma skin cancer); n (%)			
Allergic Rhinitis; n (%)			
Chronic Sinusitis; n (%)			
Bronchiectasis; n (%)			
Pneumonia; n (%)			
Chronic Bronchitis; n (%)			
Exertional Breathlessness; n (%)			
Anxiety; n (%)			
Dementia; n (%)			
Depression; n (%)			
Osteoporosis; n (%)			
Charlson-Deyo Comorbidity Index, continuous			
mean (sd)			
median [IQR]			
Charlson-Deyo Comorbidity Index, categorical			
0; n (%)			
1; n (%)			
2; n (%)			
3+; n (%)			
Acute Liver Injury or Failure; n (%)			
Chronic Kidney Disease (without ESRD); n (%)			
End Stage Renal Disease; n (%)			
Rheumatologic Disease; n (%)			

	Tio/Olo	Umecl/Vi	Standardized Difference (95% CI)
Peptic Ulcer Disease; n (%)			
Gastroesophageal reflux disease (GERD); n (%)			
Type 1 Diabetes Mellitus; n (%)			
Type 2 Diabetes Mellitus; n (%)			
Type 1 or Type 2 Diabetes with no chronic complications; n (%)			
Type 1 or Type 2 Diabetes with chronic complications; n (%)			
Mild Liver Disease; n (%)			
Moderate to Severe Liver Disease; n (%)			
Renal Disease; n (%)			
Metastatic Solid Tumor; n (%)			
HIV/AIDS; n (%)			
Hemiplegia or Paraplegia; n (%)			
Lifestyle			
Smoking Related Claim or Intervention; n (%)			
Vaccination for Influenza; n (%)			
Vaccination for Pneumococcus; n (%)			
Respiratory Function Procedures/Tests			
Pulmonary function tests; n (%)			
Six-minute walk test; n (%)			
Chest X-ray; n (%)			
Chest HRCT; n (%)			

*Tio/Olo, tiotropium/olodaterol; Umecl/Vi, umeclidinium, vilanterol.*

**Table 3.** Absolute Standardized Differences as Measured in the Unmatched vs. Matched Cohorts

	Abs. Std. Diff. (Unmatched)	Abs. Std. Diff. (Matched)	Change	Change (%)
Demographics				
Age on index date				
Gender				
Region				
Insurance Type				
Year of Cohort Entry				
Oral Corticosteroids; n (%)				
Short acting muscarinic antagonist (SAMA), n (%)				
Short acting beta agonist (SABA), n (%)				
Long acting muscarinic antagonist (LAMA), n (%)				
Long acting beta agonist (LABA), n (%)				

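### In a cohort where every patient has COPD, the Charlson-Deyo COPD point records only when COPD was coded, and it mildly blurs adjustment for comorbidity

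*Combined protocol and SAP*

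**What the plan says.** **Eligibility.** Section 9.2.2 excludes a patient who "Never had COPD diagnosis on the cohort entry date or prior to cohort entry". One claim is enough: the code list ends "J44.0, J44.1, J44.9) will be defined as the presence of an inpatient or outpatient claim". Table 1 in Annex 5 words the exclusion as "No prior diagnosis of COPD any time prior using all available data". On the data available, section 9.2.1 says "The study period will be from 1 January 2008 to 31 March 2018".

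**Score.** Annex 4 builds the Charlson-Deyo index by summing items. For COPD the rule is "If the event Chronic Obstructive Pulmonary Disease Occurs within 180 days, set the score to 1.0 Otherwise, set the score to 0.0". Heart failure within 180 days also scores 1. Nothing in the plan removes the COPD item or holds it constant.

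**Use.** The propensity model (section 9.2.2, Matched Cohort) and the unmatched Cox and logistic models (section 9.7.1.3) take all covariates in section 9.3.3 except the components of the Charlson index, so the summed score stands in for them. Table 2 reports the index as continuous and, under "Charlson-Deyo Comorbidity Index, categorical", as 0, 1, 2 and 3+.

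**Window.** Section 9.2.1 defines the baseline as "the 180-day period that ends 1 day prior to the cohort entry date used to assess covariate information", and section 9.7.1.1 likewise uses the 180 days preceding the index date. Section 9.3.3 says "Covariates will be identified based on data recorded within 180 days prior to or on the index date". The first two exclude the index date; the third includes it.

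**The concern.** An item of a comorbidity score should separate patients who have a condition from those who do not. Here all patients have the condition, and the item separates them by whether a COPD claim happens to fall in a 180-day window. That is a feature of coding and contact with care.

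Two things are at stake. In the models, one point for recent COPD coding is exchanged at par with one point for heart failure or dementia, so patients with different comorbidity can look alike to the propensity score. In Table 2, the index categories do not mean what a reader will take them to mean: 0 is not simply COPD without other disease.

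**Working it through.** The plan states no figure for this point. The feasibility counts in section 9.5 add up (3,889 + 10,862 = 14,751) but say nothing about when COPD was coded. The check is therefore a comparison of two rules, then an illustration of size on assumed inputs.

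**Step 1: the two look-backs.** Eligibility reaches back to January 2008. A patient entering at the start of selection (17 November 2015) can qualify on a claim almost eight years old, and one entering in March 2018 on a claim about ten years old. The score looks back 180 days. A qualifying claim can therefore lie outside the scoring window, and the item need not equal 1 for everyone.

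**Step 2: scores under the rule.** Let C be the sum of the other items. The score is C + 1 with a COPD code in the window and C without one.

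| Other items (C) | COPD coded in window | No COPD code in window |
|---|---|---|
| 0 | 1 | 0 |
| 1 | 2 | 1 |
| 2 | 3 | 2 |

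Heart failure with only an old COPD code gives 1 + 0 = 1. Uncomplicated COPD coded recently gives 0 + 1 = 1. A score of 0 requires that no COPD code falls in the window. These results hold whether or not the index date is in the window.

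**Step 3: share of score variance.** Assumptions: q is the share of patients with a COPD code in the window, SD is the standard deviation of C, and the two are independent. The documents give neither input. The item has variance q(1 - q), and its share of total variance is q(1 - q) / [q(1 - q) + SD²].

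| q | q(1 - q) | SD 1.0 | SD 1.5 | SD 2.0 |
|---|---|---|---|---|
| 0.80 | 0.16 | 13.8% | 6.6% | 3.8% |
| 0.90 | 0.09 | 8.3% | 3.8% | 2.2% |
| 0.95 | 0.0475 | 4.5% | 2.1% | 1.2% |
| 1.00 | 0 | 0% | 0% | 0% |

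For example, at q = 0.80 and SD = 1: 0.16 / 1.16 = 13.8%.

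**Step 4: apparent imbalance from timing alone.** If the arms have identical C but recent-coding shares q1 and q0, the standardised difference in the score is (q1 - q0) divided by the pooled SD of the score. For SD from 1.0 to 2.0:

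- 0.95 against 0.90: 0.048 to 0.025
- 0.90 against 0.80: 0.094 to 0.049
- 0.90 against 0.70: 0.187 to 0.098

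**Step 5: with the item removed.** Two patients with the same C get the same score, and both quantities in Steps 3 and 4 fall to zero.

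**The case against.** **The item may be nearly constant.** Section 9.2.1 says baseline data will be used to confirm eligibility, which could suggest that COPD is always coded in the baseline. It does not say so, and section 9.2.2 and Table 1 explicitly allow earlier claims. What stands is that most initiators of a COPD inhaler may well have a recent COPD claim. The effect would then be small and the categories would mostly just move up by one.

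**Other covariates carry the same information.** A reader might infer that the index is the only Charlson information in the models. The documents do not support that. Insulin, antidiabetic drugs, anticoagulants, all-cause hospitalisation and others stay in on any reading. Section 9.3.3 also lists kidney, diabetes and liver measures defined differently from the scored ones, and it is unclear whether they count as components. Nor can one infer that balancing would leave most of a difference in COPD recency in place: the propensity score also includes inhaled drugs, oxygen, pulmonary function tests and respiratory hospitalisation, which may track recency.

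**Newly diagnosed patients.** It is tempting to say that patients first coded at initiation score 0. That holds only if the index date is outside the window, which the plan leaves unresolved. It is equally tempting to read the item as new against established COPD. A patient first coded a month before entry and one coded for ten years with a recent claim both score 1, so it is not that.

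**Effect on the hazard ratio.** Probably small. Suppose 80% are coded recently in one arm and the odds ratio between arms is 0.7; the other share is 2.8/3.8 = 73.7%. If recent coding carried a discontinuation hazard ratio of 1.5, leaving it wholly unadjusted would shift the treatment hazard ratio by about (1 + 0.5 × 0.80) / (1 + 0.5 × 0.737) = 1.400/1.368 = 1.023. At 1.2 the factor is 1.160/1.147 = 1.011. Every input is assumed.

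**Table 2.** Calling the table uninterpretable would go too far, since the individual conditions are listed separately. The objection concerns the index categories only.

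**It is the named index.** Keeping the COPD item preserves comparability with standard scores. That is a real but minor benefit, and a footnote meets it.

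**Conclusion.** The point holds. By the plan's own rules, the COPD item can vary in this cohort only with the timing of COPD claims, and the index carries it into the propensity and multivariable models and into the Table 2 categories. This much needs no assumption beyond the item using the claim-based COPD definition of section 9.2.2.

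The consequence is a mild blurring of adjustment for comorbidity. Its size cannot be fixed from the documents. With 80-95% of patients coded recently and an SD of 1-2 for the other items, the COPD item is about 1-14% of score variance, and nothing if all are coded recently. A material bias in the primary hazard ratio is not shown. The change is worth making because the definition is wrong for this cohort and costs little to correct.

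**What to change.** - **Annex 4:** delete the COPD item from the Charlson-Deyo index.
- **Section 9.3.3 and Tables 2-3:** add *COPD claim in the 180-day baseline (yes/no)* as a separate covariate. If the index enters the models linearly, the planned model is the special case in which this covariate and the index share one coefficient, so no information is lost.
- **Table 2:** report the index categories without COPD, with a footnote that values are lower than standard Charlson-Deyo scores.
- **Window:** reconcile sections 9.2.1 and 9.7.1.1 (index date excluded) with section 9.3.3 (index date included), and apply the one resulting window to this variable.

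The new covariate captures recent COPD coding and should be described as such; it does not distinguish new from established COPD.

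The cost is one deleted line, one covariate with its table rows, one more model parameter, a footnote and the amendment that section 9.8 requires for changes. No patient is lost, no further data are needed, and the study question is unchanged. Direct comparability with published scores that count COPD is given up.

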**Comorbidities/Symptoms**

- History of All-Cause Hospitalization
- History of Emergency Department Visit
- History of Hospitalization due to Respiratory Condition
- Acute Myocardial Infarction
- Angina Pectoris
- Peripheral Vascular Disease
- Heart Failure
- Hypertension
- Upper Respiratory Infection
- Lower Respiratory Infection
- Cardiac Arrhythmias
- Cerebrovascular Disease
- All Cancers (except nonmelanoma skin cancer)
- Allergic Rhinitis
- Chronic Sinusitis
- Bronchiectasis
- Pneumonia
- Chronic Bronchitis
- Exertional Breathlessness
- Anxiety
- Dementia
- Depression
- Osteoporosis
- Charlson Deyo Comorbidity Index
- Acute Liver Injury or Failure
- Chronic Kidney Disease (without ESRD)
- End Stage Renal Disease
- Rheumatic Disease
- Peptic Ulcer Disease
- Gastroesophageal Reflux Disease
- Type 1 Diabetes Mellitus
- Type 2 Diabetes Mellitus
- HIV/AIDS
- Hemiplegia or Paraplegia

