Acute Liver Injury or Failure	
1 Inpatient or 1 Outpatient
 
Diagnosis Code (Any Position), ICD-9 is any of: { “570”, “864.0”, “864.00”, “864.01”, “864.02”, “864.03”, “864.04”, “864.05”, “864.09”, “864.1”, “864.10”, “864.11”, “864.12”, “864.13”, “864.14”, “864.15”, “864.19” }
 
Diagnosis Code (Any Position), ICD-10 is any of: { “K72.0”, “K72.00”, “K72.01”, “K72.9”, “K72.90”, “K72.91”, “S36.11”, “S36.112”, “S36.112A”, “S36.112D”, “S36.112S”, “S36.113”, “S36.113A”, “S36.113D”, “S36.113S”, “S36.114”, “S36.114A”, “S36.114D”, “S36.114S”, “S36.115”, “S36.115A”, “S36.115D”, “S36.115S”, “S36.116”, “S36.116A”, “S36.116D”, “S36.116S”, “S36.118”, “S36.118A”, “S36.118D”, “S36.118S”, “S36.119”, “S36.119A”, “S36.119D”, “S36.119S” }

Chronic Kidney	1 Inpatient or 2 Outpatient (30 – 365 days apart)

Disease (without ESRD)	
Diagnosis Code (Any Position), ICD-9 is any of: { “585.1”, “585.2”, “585.3”, “585.4” }
 
Diagnosis Code (Any Position), ICD-10 is any of: { “N18.1”, “N18.2”, “N18.3”, “N18.4” }
 
Procedure Code (Any Position), CPT and HCPC is any of: { “G0420”, “G0421”, “G8487”, “G8771” }

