End Stage Renal Disease	
1 Inpatient or 2 Outpatient (30 – 365 days apart)
 
Diagnosis Code (Any Position), ICD-9 is any of: { “403.01”, “403.91”, “458.21”, “585.5”, “585.6”, “996.56”, “996.68”, “996.73”, “V42.0”, “V45.1”, “V45.11”, “V45.12”, “V56”, “V56.0”, “V56.1”, “V56.2”, “V56.3”, “V56.31”, “V56.32”, “V56.8” }
 
Diagnosis Code (Any Position), ICD-10 is any of: { “I12.0”, “N18.5”, “N18.6”, “T86.10”, “T86.11”, “T86.12”, “Z49.01”, “Z49.02”, “Z49.31”, “Z49.32”, “Z91.15”, “Z94.0”, “Z99.2” }
 
Procedure Code (Any Position), ICD-9 is any of: { “55.69”, “55.6”, “38.95”, “39.27”, “39.42”, “39.43”, “39.95”, “54.98” }
 
Procedure Code (Any Position), ICD-10 is any of: { “05HY33Z”, “06HY33Z”, “0TS00ZZ”, “0TS10ZZ”, “0TY00Z0”, “0TY00Z1”, “0TY00Z2”, “0TY10Z0”, “0TY10Z1”, “0TY10Z2”, “3E1M39Z”, “5A1D00Z”, “5A1D60Z” }
 
Procedure Code (Any Position), CPT and HCPC is any of: { “36145”, “36800”, “36810”, “36815”, “36825”, “36830”, “36831”, “36832”, “36833”, “50323”, “50325”, “50327”, “50328”, “50329”, “50340”, “50360”, “50365”, “90918”, “90919”, “90920”, “90921”, “90922”, “90923”, “90924”, “90925”, “90935”, “90937”, “90939”, “90940”, “90945”, “90947”, “90951”, “90952”, “90953”, “90954”, “90955”, “90956”, “90957”, “90958”, “90959”, “90960”, “90961”, “90962”, “90963”, “90964”, “90965”, “90966”, “90967”, “90968”, “90969”, “90970”, “90989”, “90993”, “90997”, “90999”, “93990”, “99512”, “A4653”, “A4656”, “A4657”, “A4670”, “A4671”, “A4672”, “A4673”, “A4674”, “A4680”, “A4706”, “A4707”, “A4708”, “A4709”, “A4712”, “A4714”, “A4719”, “A4720”, “A4721”, “A4722”, “A4723”, “A4724”, “A4725”, “A4726”, “A4728”, “A4730”, “A4736”, “A4737”, “A4740”, “A4750”, “A4755”, “A4760”, “A4765”, “A4766”, “A4770”, “A4771”, “A4773”, “A4774”, “A4802”, “A4860”, “A4870”, “A4890”, “A4911”, “A4913”, “A4918”, “A4928”, “A4929”, “C1881”, “E1500”, “E1520”, “E1530”, “E1540”, “E1550”, “E1560”, “E1570”, “E1575”, “E1580”, “E1600”, “E1610”, “E1615”, “E1620”, “E1625”, “E1634”, }

	“E1635”, “E1636”, “E1637”, “E1639”, “E1699”, “G0257”, “G0308”, “G0309”, “G0310”, “G0311”, “G0312”, “G0313”, “G0314”, “G0315”, “G0316”, “G0317”, “G0318”, “G0319”, “G0320”, “G0321”, “G0323”, “G0324”, “G0325”, “G0326”, “G0327”, “G8727”, “G9013”, “G9014”, “J0635”, “J0636”, “S2065”, “S9335”, “S9339”, “E1638”, “G0322” }

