Renal Disease	
1 Inpatient or 2 Outpatient (30 – 365 days apart)
 
Diagnosis Code (Any Position), ICD-9 is any of: { “582”, “582.0”, “582.1”, “582.2”, “582.4”, “582.8”, “582.81”, “582.89”, “582.9”, “583”, “583.0”, “583.1”, “583.2”, “583.4”, “583.6”, “583.7”, “585”, “585.1”, “585.2”, “585.3”, “585.4”, “585.5”, “585.6”, “585.9”, “586”, “588”, “588.0”, “588.1”, “588.8”, “588.81”, “588.89”, “588.9” }
 
Diagnosis Code (Any Position), ICD-10 is any of: { “I12.0”, “I13.1”, “N03.2”, “N03.3”, “N03.4”, “N03.5”, “N03.6”, “N03.7”, “N05.2”, “N05.3”, “N05.4”, “N05.5”, “N05.6”, “N05.7”, “N18.1”, “N18.2”, “N18.3”, “N18.4”, “N18.5”, “N18.6”, “N18.9”, “N25.0”, “Z49.0”, “Z49.01”, “Z49.02”, “Z94.0”, “Z99.2” }

Metastatic Solid Tumors	
1 Inpatient or 2 Outpatient (30 – 365 days apart)
 
Diagnosis Code (Any Position), ICD-9 is any of: { “196”, “196.0”, “196.1”, “196.2”, “196.3”, “196.5”, “196.6”, “196.8”, “196.9”, “197”, “197.0”, “197.1”, “197.2”, “197.3”, “197.4”, “197.5”, “197.6”, “197.7”, “197.8”, “198”, “198.0”, “198.1”, “198.2”, “198.3”, “198.4”, “198.5”, “198.6”, “198.7”, “198.8”, “198.81”, “198.82”, “198.89”, “199”, “199.0”, “199.1” }
 
Diagnosis Code (Any Position), ICD-10 is any of: { “C77.0”, “C77.1”, “C77.2”, “C77.3”, “C77.4”, “C77.5”, “C77.8”, “C77.9”, “C78”, “C78.0”, “C78.00”, “C78.01”, “C78.02”, “C78.1”, “C78.2”, “C78.3”, “C78.30”, “C78.39”, “C78.4”, “C78.5”, “C78.6”, “C78.7”, “C78.8”, “C78.80”, “C78.89”, “C79”, “C79.0”, “C79.00”, “C79.01”, “C79.02”, “C79.1”, “C79.10”, “C79.11”, “C79.19”, “C79.2”, “C79.3”, “C79.31”, “C79.32”, “C79.4”, “C79.40”, “C79.49”, “C79.5”, “C79.51”, “C79.52”, “C79.6”, “C79.60”, “C79.61”, “C79.62”, “C79.7”, “C79.70”, “C79.71”, “C79.72”, “C79.8”, “C79.81”, “C79.82”, “C79.89”, “C79.9”, “C80”, “C80.0”, “C80.1”, “C80.2” }

HIV/AIDS	
1 Inpatient or 2 Outpatient (30 – 365 days apart)
 
Diagnosis Code (Any Position), ICD-9 is any of: { “042”, “795.71”, “V08”, “V65.44”, “079.53” }
 
Diagnosis Code (Any Position), ICD-10 is any of: { “B20”, “Z21”, “B97.35”, “O98.7*”, “Z71.7” }

Hemiplegia or Paraplegia	
1 Inpatient or 2 Outpatient (30 – 365 days apart)
 
Diagnosis Code (Any Position), ICD-9 is any of: { “342”, “342.0”, “342.00”, “342.01”, “342.02”, “342.1”, “342.10”, }

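### The CKD (without ESRD) covariate omits the unspecified-stage codes 585.9 and N18.9, which the plan's own Renal Disease measure counts, so some patients score Charlson renal points while recorded as having neither CKD nor ESRD

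*Combined protocol and SAP*

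**What the plan says.** Annex 4 defines three kidney measures. All three use the same claims rule: one inpatient claim, or two outpatient claims 30 to 365 days apart.

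- **CKD (without ESRD).** The diagnosis codes are "585.1”, “585.2”, “585.3”, “585.4" (ICD-9) and "N18.1”, “N18.2”, “N18.3”, “N18.4" (ICD-10). The row also accepts four procedure codes, "G0420”, “G0421”, “G8487”, “G8771".
- **End Stage Renal Disease.** Within the 585 and N18 families it takes 585.5, 585.6, N18.5 and N18.6 (the ICD-9 run reads "585.5”, “585.6”, “996.56"). It adds a long list of dialysis and transplant codes.
- **Renal Disease.** It lists the staged codes and the unspecified-stage codes: "585.4”, “585.5”, “585.6”, “585.9”, “586" in ICD-9 and "N18.4”, “N18.5”, “N18.6”, “N18.9”, “N25.0" in ICD-10.

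Renal Disease feeds the Charlson-Deyo index: "If the event Renal Disease Occurs within 180 days, set the score to 2.0".

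Section 9.3.3 lists CKD (without ESRD), ESRD and the Charlson-Deyo index as covariates, but not Renal Disease. The propensity model (section 9.2.2, Matched Cohort) and the multivariable models (section 9.7.1.3) use all section 9.3.3 covariates except components of the Charlson index. In Annex 5, Tables 2 and 3 have separate rows for CKD, ESRD and Renal Disease. The documents give no reason for leaving the unspecified-stage codes out of the CKD row.

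**The concern.** The plan gives two different answers about the same patient. Someone whose qualifying renal claims are all coded N18.9 has renal disease for the Charlson index and no kidney disease in either of the two kidney covariates. Section 9.12 treats the section 9.3.3 covariates as hypothesised confounders, so these patients would be matched and adjusted as free of CKD if CKD stays in the models. If CKD is instead read as a Charlson component and dropped, the error still reaches Tables 2 and 3. Those tables serve the first secondary objective and the balance check, and a near-zero standardised difference on an incomplete flag says less about CKD balance than it appears to.

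The label raises a second, smaller issue. Nothing in the row sets CKD to no when the ESRD row is met, so a patient with qualifying N18.4 and N18.6 claims counts in both rows.

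**Working it through.** The plan states no figure on this point, so there is none to reproduce. The main check is a comparison of code lists.

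**Step 1: the 585 and N18 families, row by row (Annex 4).**

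| Code | CKD row | ESRD row | Renal Disease row |
|---|---|---|---|
| 585.1-585.4, N18.1-N18.4 | yes | no | yes |
| 585.5, 585.6, N18.5, N18.6 | no | yes | yes |
| 585.9 | no | no | yes |
| N18.9 | no | no | yes |
| 585 (heading code) | no | no | yes |

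Within these families, Renal Disease minus (CKD plus ESRD) leaves exactly 585, 585.9 and N18.9. Every CKD diagnosis code is in the Renal Disease row. Because the claims rule is the same in all three rows, the mismatch comes from the code lists alone.

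**Step 2: what happens to a patient.** With only 585.9 or N18.9 as qualifying renal claims, and none of the four procedure codes, the record reads Renal Disease yes (+2 Charlson points), CKD no, ESRD no. Mixed coding can have the same result. One outpatient N18.3 claim and one outpatient N18.9 claim 60 days later meet Renal Disease, but only one of the two claims counts towards CKD.

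**Step 3: all codes, not only these families.** Renal Disease lists 32 ICD-9 and 27 ICD-10 codes. Of these, 26 and 16 are in neither the CKD nor the ESRD diagnosis list. Removing 585, 585.9 and N18.9 leaves 24 and 15, such as 582.x, 583.x, 586, 588.x, N03.x and N05.x. In the other direction, the ESRD row has entries that Renal Disease lacks, such as V56.x, T86.1x and its procedure codes.

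**Step 4: illustration of size.** Every input here except 3,889 (section 9.5) is an assumption: true CKD prevalence p1 of 0.10 to 0.14 in the Stiolto arm, p0 two percentage points lower in the Anoro arm, 30-50% of CKD patients carrying only unspecified-stage codes (flag sensitivity s of 0.7 to 0.5), and specificity 1.

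- Missed Stiolto initiators: 3,889 × 0.10 × 0.30 = 117, up to 3,889 × 0.14 × 0.50 = 272.
- True CKD among the unflagged in an arm: r = p(1 − s)/(1 − s·p). After balance on the flag, the residual difference is d = (1 − s·p1)(r1 − r0).

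| p1, p0 | s | r1 | r0 | d | share of the 0.02 left |
|---|---|---|---|---|---|
| 0.10, 0.08 | 0.7 | 0.0323 | 0.0254 | 0.0064 | 32% |
| 0.14, 0.12 | 0.7 | 0.0466 | 0.0393 | 0.0066 | 33% |
| 0.10, 0.08 | 0.5 | 0.0526 | 0.0417 | 0.0104 | 52% |
| 0.14, 0.12 | 0.5 | 0.0753 | 0.0638 | 0.0106 | 53% |

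- As a standardised difference, d is about 0.0066/0.344 = 0.02 to 0.0104/0.293 = 0.04.
- Suppose CKD itself carried a discontinuation hazard ratio h. The bias factor on the treatment hazard ratio is roughly [1 + (h − 1)p1]/[1 + (h − 1)(p1 − d)]. With h = 1.5 this runs from 1.050/1.0468 = 1.003 to 1.070/1.0647 = 1.005. With h = 2.0 it runs from 1.100/1.0936 = 1.006 to 1.100/1.0896 = 1.010.

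All of these take the CKD flag as the only adjuster. They are upper illustrations before any Charlson adjustment.

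**The case against.** The strongest reply is that renal burden is handled elsewhere. A patient coded only N18.9 gets 2 Charlson points, the index is itself a covariate, and Renal Disease has its own row in Tables 2 and 3, so the balance check does see these patients. If CKD is a Charlson component, it leaves the models and the modelling effect is nil. This stands as to size. It does not cure the covariate: 2 Charlson points can equally come from hemiplegia or from two one-point conditions, and the CKD row is reported under its own name.

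It can also be said that the lists already split CKD from ESRD by stage, which is one reading of the label, and that a patient flagged on both remains identifiable through the ESRD covariate. That makes the overlap a minor matter, and no size can be given for it. An unspecified-stage code does not by itself show absence of ESRD, so adding it is a judgement; the exclusion line in the fix addresses this.

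Finally, section 9.12 provides for medical review of the code lists and section 9.8 allows measure definitions to be modified. These are routes to a correction, not reasons for the omission.

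A reader might infer that Renal Disease must exceed CKD plus ESRD in Table 2 with no explanation. The documents do not support this. Step 3 shows that each side holds codes the other lacks, and patients counted in both CKD and ESRD raise that sum. The rows will not reconcile, but the direction is unknown, and the fix would not make them agree.

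**Conclusion.** The inconsistency is real and certain at the level of the code lists: 585.9 and N18.9 count as renal disease for the Charlson index and as neither CKD nor ESRD in section 9.3.3. The CKD covariate is misclassified as written. The missing codes lower its reported prevalence, while the lack of an ESRD exclusion raises it, so Tables 2 and 3 misstate both prevalence and balance.

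A reader might infer that a third to a half of any CKD confounding survives in the primary hazard ratio. The documents do not support that. They give no CKD prevalence, no code frequencies and no between-arm difference, and the 32-53% ignores the Charlson score. Under the same assumptions the residual is 0.64 to 1.06 percentage points, and the hazard ratio would move by about 0.3-0.5% (CKD hazard ratio 1.5) or 0.6-1.0% (2.0) before Charlson adjustment. The effect on the primary result is therefore probably small. It also depends on whether CKD counts as a Charlson component. The plan does not say; the component that Annex 4 names is Renal Disease.

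The point is worth correcting as a cheap repair to a named covariate. It is not a threat to the primary conclusion.

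**What to change.** In the CKD (without ESRD) row of Annex 4, add 585.9 and N18.9, and add the heading code 585 for consistency with the Renal Disease row. Add one line setting CKD (without ESRD) to no for any patient who meets the ESRD row, so that the covariate matches its label and the two covariates are mutually exclusive. If the restriction to staged codes was deliberate, state the reason instead.

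The cost is three codes and one exclusion line, documented as a protocol amendment under section 9.8. No new data are needed.
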